### C. RESEARCH DESIGN AND METHODS

#### C1. Study Overview: GMI for Homeless Veterans in VA housing

The primary objective of this 4-year prospective, randomized, between groups, repeated measures effectiveness trial is to compare (a) GMI to a (b) control treatment condition (CT) for dually diagnosed Veterans with SUDs in VA housing. *The study intervention, GMI, will serve Veterans who attend a workshop addressing their substance abuse and mental health problems regardless of their level of commitment for undertaking behavioral change. This study is designed to recruit dually diagnosed Veterans in two primary VA housing programs, HUD-VASH and GPD. The programs share in common that they receive Veterans with substance use, and the dynamic of moving toward preserving housing even when lapse or relapse occurs. According to [name], National Director of VA GPD, GPD will be moving more “in-line” with VA Housing First over time (personal communication, Nov. 7, 2013). Thus, there is no a-priori reason to suggest that participants who volunteer to enroll in the study will experience differential benefits based on where they reside, and this study is not powered to test for such differences.* We will conduct a process evaluation to document formative (e.g., plan for intervention), process, and summative indicators. A logic model containing our plan for documenting aims, inputs, outputs, outcomes, and impacts is presented in Table 5 (below). Our third aim includes estimation of cost (direct and indirect costs, workload measures, costs of capital). Estimated costs of the intervention will be used in implementation and dissemination research. A racially/ethnically diverse sample of 186 Veterans with current alcohol/drug dependence or abuse will be recruited. Male and female Veterans with co-existing DSM-IV-TR Axis I disorders (e.g., MDD, PTSD) will be eligible. Participants will be randomized using a variant of block randomization, where “recruitment week” is the unit of randomization; this will facilitate the process of forming “closed treatment groups” (e.g., approximately 6 members). Participants will be randomized to participate in 4 consecutive 90-minute GMI or CT sessions. *Timing for conducting GMI/CT and completion of assessments is as follows: Consent & Baseline interviews (Week 1) → GMI or CT (4 sessions back-to-back; Week 2) → one-month follow-up; Week 4) → 3-month follow-up (Week 12) → 6-month follow-up (Week 24).*

| Characteristic | GMI (n = 59) | TAU (n = 59) |
|----------------|--------------|--------------|
| Mean age (SD)  | 52.9         | 51.1         |

|                    |          |          |
|--------------------|----------|----------|
| Gender             |          |          |
| Male               | 54 (92%) | 54 (92%) |
| Female             | 5 (8%)   | 5 (8%)   |
| Race               |          |          |
| Caucasian          | 27 (46%) | 22 (37%) |
| African-American   | 32 (54%) | 36 (61%) |
| Hispanic           | 0 (0%)   | 1 (2%)   |
| Education          |          |          |
| ≤ High School Grad | 28 (48%) | 24 (40%) |
| College            | 18 (30%) | 28 (48%) |
| ≥ College graduate | 13 (22%) | 7 (12%)  |

**C2. Feasibility and Preliminary Data:** Data and clinical research presented below provide a strong foundation for the current study.

**C2a. Project 1: GMI resulted in higher treatment engagement and lower substance use compared to standard treatment**. We conducted a NIH-NIDA funded **Stage I-pilot** controlled trial comparing GMI ( $N = 50$ ) to standard treatment (ST;  $N = 51$ ) among 101 dually diagnosed psychiatric inpatients randomized to two 120-minute GMI or ST sessions. Participants were those with at least one current SUD and a nonsubstance-related major Axis I disorder. All

patients and collaterals were interviewed at 1 and 3-month follow-up. Three main outcomes of the pilot study showed that: 1) GMI reduced the number of inpatient hospital detoxification re-admissions after initial hospitalization compared to ST: GMI participants were re-admitted to inpatient detoxification fewer times (GMI: 6.8%; ST: 25.6%;  $p = .03$ ) during the 3-month follow-up period; 2) Participants in GMI attended more outpatient aftercare treatment sessions compared to participants in ST ( $M=5.7$  [SD=6.7] vs.  $M=2.5$  [1.9];  $p=.001$ ) and attended more 12-Step or AA/NA self-help sessions ( $M=21.7$  [18.8] vs.  $M=6.8$  [6.8];  $p<.01$ ) by 3-month follow-up; and 3) GMI was associated with reduced substance use: Participants in GMI drank less alcohol (measured in standard ethanol content units), compared to their counterparts in ST by 3-month follow-up ( $M=117.3$  [182.8] vs.  $M=262.3$  [312.9],  $p=.04$ ), engaged in less binge drinking ( $M=4.6$  [3.2] vs.  $M=13.9$  [10.5],  $p=.001$ ) and had fewer days of illicit drug use ( $M=5.2$  [7.2] vs.  $M=13.0$  [12.0];  $p=.01$ ) at 1-month follow-up. A smaller *proportion* of GMI participants reported binge drinking (34.1% in GMI vs. 55.8% in ST,  $p = .02$ ) at the 3-month follow-up.

**II. Project 2: GMI resulted in lower alcohol use, higher outpatient treatment attendance, and greater participant change talk compared to TAU**. In her CDA-2 (CDA-2-016-08S) titled: ‘Impact of Group Motivational Interviewing on Dually Diagnosed Veterans’, [name] compared GMI to treatment-as-usual (TAU) among 118 Veterans with current alcohol dependence or abuse, an accompanying drug abuse disorder, and a co-existing Axis I psychiatric disorder recruited through the Charleston VAMC Substance Abuse Treatment Center (SATC). Participants were randomized to GMI ( $n=59$ ) or TAU ( $n=59$ ). All participants were interviewed at 1 and 3-month follow-up. Patients attended four 75- minute sessions of GMI or TAU across 4 consecutive days. TAU was designed as a psycho-educational group (e.g., addiction as a chronic disease). [name] modified her GMI protocol for application in the VA outpatient SATC, trained five clinicians to provide interventions, and provided consultation for continued therapist adherence/competence to the protocol. Participant characteristics and DSM-IV-TR substance use and comorbid Axis I diagnoses are listed in Tables 1 and 2. A study coordinator blind to study conditions evaluated participants at baseline and at a 1 and 3-month follow-up. Treatment utilization was assessed via CPRS. Researchers counted the number of outpatient substance abuse treatment encounters and individual mental health treatment appointments with mental health staff (e.g., case-managers, psychiatrists, psychologists) that occurred in the 3 months following the patient’s consent (at the Charleston VAMC only). Substance use was assessed using the Time-Line Follow Back. We measured daily and peak alcohol consumption in standard drinks at 3-month follow-up. Data analyses were conducted using ANCOVA with ZINB distribution. Although analyses remain ongoing, preliminary results for primary outcome variables reveal the following: **A) Participants in GMI attended significantly more general outpatient mental health treatment sessions compared to TAU** by 3-month follow up,  $b = .944$  (.307),  $t = 3.079$ ,  $p < .001$ ; Cohen’s  $d=.54$ . No baseline differences in treatment engagement were found.

| Table 2. DSM-IV-TR Substance Use             | GMI   | TAU   |
|---|--------------|--------------|
| Alcohol Abuse/dependence                            | 59
(100%) | 59
(100%) |
| Opioid dependence                                   | 1 (16%)      | 3 (5%)       |
| Sedative/hypnotic dependence                        | 1 (2%)       | 0 (0%)       |
| Cocaine abuse/dependence                            | 16 (27%)     | 18 (31%)     |
| Marijuana abuse/dependence                          | 7 (12%)      | 8 (14%)      |
| DSM-IV Comorbid Axis I Diagnoses             |              |              |
| Depressive Disorders                                | 30 (51%)     | 30 (51%)     |
| Bipolar I/II Disorders                              | 4 (7%)       | 2 (3%)       |
| Anxiety Disorders (PTSD, panic, GAD, social phobia) | 30
(51%)  | 32 (54%)     |
| Mood Disorders NOS                                  | 2 (3%)       | 0 (0%)       |
| Substance Induced Mood Disorder                     | 7 (12%)      | 3 (5%)       |

|                                  |         |         |
|----------------------------------|---------|---------|
| Schizophrenia/psychotic Disorder | 1 (2%)  | 2 (3%)  |
| Schizoaffective Disorder         | 1 (2%)  | 1 (2%)  |
| Borderline Personality Disorder  | 1 (2%)  | 0 (0%)  |
| Antisocial Personality Disorder  | 0 (0%)  | 1 (2%)  |
| No co-existing Axis I Disorder   | 6 (10%) | 8 (14%) |

[figure not shown]
**B) Participants in GMI relative to TAU consumed less alcohol** in standard drinks,  $b=-155.3$  (70.9),  $t=-2.19$ ,  $p=.03$ ; Cohen's  $d=.36$ ) and drank fewer standard drinks in terms of their peak (highest) drinking day,  $b=-4.78$  (2.03),  $t=-2.4$ ,  $p=.02$ . No baseline differences

between groups were found on alcohol consumption.

**C) Change talk mediates the effect of GMI and substance use outcome and is more prevalent in GMI compared to TAU.** Change talk is client language in favor of change and its enhancement is the primary goal of MI (e.g., "I want to quit drinking for my family"). Change talk variables, such as "ability" language and its underlying dimensions (e.g., 'desire, reason, need, commitment, taking steps') underlie the efficacy of MI, such that stronger change talk predicts substance use. Therapist adherence to MI increases change talk, which serves as a mediator between therapist behavior and lowering alcohol use consumption. Studies on change talk indicate that it is the strongest indicator of mechanism of action in MI contributing to outcome. GMI activities intentionally evoke change talk by design, although studies examining change talk in GMI have not been conducted. The

presence of change talk in GMI provides evidence showing that similar mechanisms of action that are present in MI are also present in GMI. Using a coding manual (adapted from the Motivational Interviewing Treatment Integrity (MITI) Code, version 3.1.1.), two trained raters blind to treatment condition coded 138 audio recorded GMI/TAU sessions for change talk [GMI=68; TAU=70], 8 on which they overlapped for establishing rater reliability. ICC's were excellent, ranging from lowest .92 to highest .99 across all six change talk categories.

Figure 3. Overall between Group Change Talk across the Four Sessions

Using group clustered latent growth models examining between group frequency of change talk ratings, with the exception of 'commitment' [ $t=1.8$ ;  $p=.07$ ], all types of change talk ('desire' [ $t=4.9$ ;  $p<.001$ ], 'ability' [ $t=3.0$ ;  $p=.002$ ], 'reason' [ $t=5.1$ ;  $p<.001$ ], 'need' [ $t=3.8$ ;  $p<.001$ ], and 'taking steps' [ $t=5.1$ ;  $p<.001$ ]) was higher in GMI relative to TAU and remained above TAU across all 4 sessions, as seen in Figure 3. To examine whether change talk predicts substance use outcome, we conducted a group clustered path mediation analysis. By 3-month follow up, 'Ability' change talk predicted less alcohol consumption (Estimate:  $-71.5$ ; CI:  $-165.74$ ,

$-2.0$ ), while 'Need' change talk predicted greater alcohol consumption (Estimate:  $-104.9$ ; CI:  $28.0$ ,  $208.2$ ), indicating that 'Ability' should be enhanced in GMI. These data provide preliminary evidence that GMI enhances change talk and predicts substance use outcome among dually diagnosed Veterans. **Note: 19% (n=23; GMI=15/TAU=8) of [name] dually diagnosed sample (n=118) were homeless Veterans receiving VA housing services. 78% (n=18) completed all 4 treatment sessions (GMI=73%, n=11/TAU=88%, n=7); 91% (n=21) completed all study interviews (GMI= 87%, n=13/TAU=100%, n=8), showing evidence of feasibility among homeless Veterans.**

### C3. Recruitment Plan and Feasibility of Recruitment

The VA housing program of the Charleston, SC VAMC will be the primary site of recruitment, including Myrtle Beach and Savannah. As there are no competing studies, we anticipate no difficulties with recruiting the needed participants within the 30 month recruitment period. Recruitment will occur through: 1) VA housing Referrals: study personnel will attend weekly VA housing staff meetings to discuss potentially eligible patients; 2) Invitation letters: Provided IRB approval, conducting VISTA queries (every 3 months) of Veterans with VA housing admissions and a DSM-V Axis I substance use disorder diagnosis. Letters of invitation describing the study and its eligibility requirements will be sent out by study personnel to patients so they who can return-mail their interest in participating; 3) General referrals: We will recruit participants who have not formally entered SUD treatment from Tracks 1 and 2 'pre-treatment' groups of the Charleston VAMC SATC outpatient program, and receive referrals from VA physicians and clinic staff, social workers, nurses, mental healthcare physicians, or patients themselves in response to study flyers. Approved recruitment flyers will be posted in prominent locations in the study clinics; 4) Interest (wait) list referrals: consisting of names and contact information of patients waiting to enroll in HUD-VASH. Wait list referrals are comparable to participants in HUD-VASH; the only exception being that they applied when vouchers were not available. Only study personnel will recruit participants to prevent potential coercion by VA housing staff.

**Feasibility of Recruitment:** This study requires 186 Veterans currently in VA housing or newly entering VA housing, but not yet housed. *We will recruit 50% (n = 93) of participants from HUD-VASH and the other 50% (n = 93) from GPD within 30 months between Year 1, Month 7 and Year 3, Month 12 (see Gantt chart in Table 6 of Project Timeline).* As of 10/2013 there are 385 vouchers (i.e., participants currently enrolled in HUD-VASH), 65 anticipated new vouchers for Fiscal Year 2014 ([name], personal communication, 10/2014), and 41 (x 2.5 years) patients on the interest list. Additionally there are ~104 new clients entering the system annually due to participant departure/turnover. *Taken together, at least 813 patients (385 + 65+ 41\*2.5 years [103] +104\*2.5 years [260] = 813) will be screenable over the course of 2.5 recruitment years. 50 to 60% of HUD-VASH participants have an SUD. Taking the most conservative estimate of participants having any SUD (i.e., 50%) provides 407 participants eligible (813\*.50 = 407); a figure well above the 186 participants needed for the study. 80% of residents in VA GPD have an SUD. In the GPD program, there are approximately 285 new (non-overlapping) admissions per year providing 570 participants eligible to participate (285\*2.5 years = 713\*.80 = 570). All combined, there are approximately 977 potentially eligible participants (407+570 = 977) during the 30 months of study recruitment, resulting in 32 new admissions, on average, per month.*

**Attrition and Retention:** This study's recruitment of 186 subjects (93 per trial arm) reflects a power calculation in which up to 30% could be lost to follow up. This conservative attrition estimate is well above the 13% study drop-out rate in [name] CDA-2. Additionally, it is consistent with average participant drop-out rates in the addiction field, and is well within NIDA recommended guidelines of at least 80% retention in research. This rate is conservative given that the majority of VA housing patients in the current protocol will already be "engaged" in ongoing VA services and these patients tend to remain in VA care.

**Participant Payments:** *All participants will receive subject fees based on an increasing incremental plan to enhance study retention: \$25.00 for the baseline assessment, \$25 for each of four treatment sessions, \$25 for the Booster session, \$50.00 for the one-month follow-up, \$50.00 for the 3-month follow-up, and \$50.00 for the 6-month assessment for a combined possible total of \$300.00. As participants in this study are likely to be unemployed, most will lack sufficient funds to obtain transportation to the group therapy site for the sessions.*

**C4. Participant Eligibility Criteria.** *Participants will need to meet the following inclusion criteria: Veterans currently in HUD-VASH and GPD, newly entering the program but not yet housed, or Veterans on the HUD-VASH interest (wait) list, able to comprehend English, meeting DSM-V criteria for current substance use disorder, use of substances in past 30 days prior to date of consent, able to provide informed consent, functioning at an intellectual level sufficient to allow accurate completion of all assessment instruments, and willing to commit to 4 group therapy sessions, the booster session, and baseline, 1, 3, and 6 month follow-up assessments. We will record recruitment site from where participants were derived (HUD-VASH/GPD) as well as amount of time in VA housing to explore site effects (as covariate and effect-modifier) in the analytic phase. If there are differences based on these variables, they will become covariates and adjusted in the analysis.*

**C5. Randomization Procedures.** *Participants will be assigned to GMI or CT using a block randomization procedure successful in shortening the amount of time needed to fill a group. This procedure was successfully utilized in [name] CDA. In this procedure, a set of consecutively admitted participants will be assigned to the same treatment condition with 'recruitment week' being the unit of randomization (i.e., recruitment weeks themselves are randomized). A computer randomizes recruitment weeks; therefore, all participants entering the study in a treatment week enter the same treatment condition. Since session attrition occurs infrequently (i.e., some participants may elect to not attend a particular session for various reasons) and is typically no more than 1 to 2 absent individuals, we will recruit at least 6 participants per workshop to ensure that there will be enough attendees present. Thus, we anticipate between 3 to 6 participants will attend any one session; providing a maximum of (up to) 62 workshops each containing four sessions for a maximum total of 31 workshops in GMI (124 sessions) and 31 workshops in CT (124 sessions). Once a Veteran is randomized he or she will be entered into the study and included in intent-to-treat analysis. We will track session attendance. Should there be a difference on group member attendance between treatment conditions, we will account for within session correlations of outcome by including random effects corresponding to the clusters.*

**C6. Description of Proposed Novel Intervention (see appendix for GMI treatment manual).** GMI & CT group sessions will take place in various community locations (e.g., HUD-VASH apartment complexes/GPD residential programs [e.g., Charleston Vets]).

**Group motivational Interviewing (GMI):** Following randomization, participants will be scheduled with their study therapist (see therapist training in section C8) in a closed group. GMI participants will receive four structured,

back-to-back, 90-min sessions consistent with the central principles and spirit of MI. GMI, which is based on a manualized protocol, is specifically designed for dually diagnosed Veterans. A focus of the intervention creates awareness of the relationship between the substance use and co-existing psychiatric disorder and the importance of treating both. The primary aim of GMI Session 1 is to introduce the guidelines of group behavior (e.g., the GMI normative culture), explore common emotions (e.g., anxiety, fear) associated with ambivalence to change, instill autonomy, evaluate pros/cons of substance use, and evaluate readiness/confidence to change. The primary aim of GMI Session 2 is to enhance discrepancy, a key element in building motivation for change. Participants are provided a sealed “Personalized Graphic Feedback Report” (PFR; An updated version will be engineered by Datstat Inc. and is discussed in the budget) based on the baseline assessment summarizing the participant’s drinking and drug use patterns compared to the population, combined with 12 other feedback components (e.g., SUD consequences, liver enzymes). The primary aim of GMI Session 3 is to explore and clarify goals/values, increase self-efficacy, and engage members in a discussion on the interrelationship between their substance use and co-existing psychiatric disorder. The focus of this discussion relates positive (e.g., healthy) mental health and proactive behavior, such as engaging in a productive job or structured activity, fostering relationships with friends, family, and the community, taking medication, staying clean and sober, and going to treatment with positive outcome. The primary aim of GMI Session 4 is to enhance intrinsic motivation to go to treatment and engage in productive work or other structured activities, and introduce an activity to increase self-efficacy for continuing treatment and enhancing social activities.

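### Recruitment weeks are randomised and treatment is given in closed groups, but the cluster term depends on an attendance difference and the power calculation has no design effect

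*Combined protocol and SAP*

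**What the plan says.** Allocation is by cluster. Section C1 says that the recruitment week "is the unit of randomization; this will facilitate the process of forming" closed treatment groups of about 6, and C5 confirms that "all participants entering the study in a treatment week enter the same treatment condition". C5 also says "we will recruit at least 6 participants per workshop", expects 3 to 6 attendees at a session, and sets a ceiling of 62 workshops, 31 per arm.

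On analysis, C5 offers random effects for the clusters under one condition: "Should there be a difference on group member attendance between treatment conditions, we will account for within session correlations of outcome". C12d specifies intervention group, time and their interaction. C12c describes random intercepts and slopes as heterogeneity between individuals. Neither section names a week or workshop term. C4 adds a conditional adjustment for housing programme and time in housing: "If there are differences based on these variables, they will become covariates and adjusted in the analysis".

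C11 uses a two-sided 5% test, three time points, within-participant correlation of at most 0.5 and 30% dropout. From these it reports 83% power to detect a difference of 0.4 with 65 per arm, inflated to 93 per arm. It gives no ICC, cluster size or design effect.

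The plan does handle grouping elsewhere. The exploratory change-talk mediation in C9b is group-clustered, and the earlier engagement analysis cited in C11 accounted for group nesting.

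**The concern.** Two features of the design can make outcomes correlate within a cluster: whole weeks are assigned to one arm, and treatment is delivered to intact groups. Both operate whether or not attendance differs between the arms. An attendance difference is therefore the wrong trigger, and it also makes the model depend on the data.

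If attendance is similar, the rule as written analyses a cluster-randomised trial as if individuals had been randomised. Every Aim I between-arm comparison would be affected, including the month-1 contrast that C12d calls primary. P-values would be too small and confidence intervals too narrow. The C4 covariates might absorb some between-group variance, but they are conditional and do not replace a cluster term. The AR(1) and compound-symmetry structures in C12b concern repeated measures on one person.

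Separately, the stated 83% assumes no clustering whether or not the trigger is met.

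**Working it through.** **1. Reproduce the plan's power.** C11 gives the difference in standard drinks without a standard deviation, so SD = 1 is assumed. With AR(1) correlation 0.5, the variance of a three-visit mean is (3 + 4×0.5 + 2×0.25)/9 = 5.5/9 = 0.611. Power ≈ Φ(δ/√(2×0.611/n) − 1.96):

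- n = 50, δ = 0.5: 89.2% (stated 89%)
- n = 65, δ = 0.4: 83.1% (stated 83%)

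Compound symmetry at 0.5 with three visits gives 86.5% and 79.8%. Compound symmetry with four occasions (88.5% and 82.2%), or with three visits and correlation 0.4 (89.8% and 83.7%), also comes close. Every version that fits treats participants as independent.

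**2. Check for spare sample size.** 65/0.7 = 92.9, so dropout alone gives 93 per arm. C11 then describes a further 30% inflation but ends at the same 93; a second inflation would give 93/0.7 = 133. Nothing is left over for clustering.

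**3. Cluster sizes.** 186/6 = 31 workshops in total, and 186/3 = 62. The mean retained cluster size for a participant in a group of g is m = 1 + (g − 1)(1 − loss). For groups of 6 and 3 this is 4.5 and 2.4 at 30% loss. At 13% loss, the rate C3 reports for the earlier trial, it is 5.35 and 2.74.

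**4. Type I error at month 1 with no cluster term.** The design effect is DE = 1 + (m − 1)×ICC, and the true error is 2×(1 − Φ(1.96/√DE)). The ICC is a residual, per-visit value and is assumed.

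| Loss | Group size | DE at ICC 0.02 / 0.05 / 0.10 | Type I error |
|---|---|---|---|
| 30% | 6 | 1.07 / 1.175 / 1.35 | 5.8 / 7.1 / 9.2% |
| 30% | 3 | 1.028 / 1.07 / 1.14 | 5.3 / 5.8 / 6.6% |
| 13% | 6 | 1.087 / 1.218 / 1.435 | 6.0 / 7.6 / 10.2% |
| 13% | 3 | 1.035 / 1.087 / 1.174 | 5.4 / 6.0 / 7.0% |

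A simulation of 20,000 null trials per setting agrees. The unclustered t-test rejected in 5.6/7.3/9.1% (31 groups of 6) and 5.6/5.8/7.0% (62 groups of 3) at 30% loss. A t-test on cluster means stayed at 4.7–5.2% throughout.

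**5. Power for the three-visit mean, analysed with clusters.** This is a noncentral t calculation with δ = 0.4, SE = √(2×0.611×DE/n), and n = 93×0.70 = 65.1 or 93×0.87 = 80.9 per arm. Degrees of freedom are workshops minus 2 (29 or 60). If the group effect is constant to month 6, the ICC of the mean is ICC/0.611. If it fades at the same AR(1) rate, the ICC of the mean equals the per-visit ICC.

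| Loss, group effect | Group size | ICC 0 | ICC 0.02 / 0.05 / 0.10 |
|---|---|---|---|
| 30%, constant | 6 | 80.6% | 76 / 70 / 61% |
| 30%, constant | 3 | 81.9% | 80 / 78 / 74% |
| 30%, fading | 6 | 80.6% | 78 / 74 / 68% |
| 30%, fading | 3 | 81.9% | 81 / 79 / 77% |
| 13%, constant | 6 | 88% | 84 / 77 / 67% |
| 13%, constant | 3 | 89% | 88 / 85 / 81% |

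The step from about 83% to 80.6% or 81.9% at ICC 0 comes from the degrees of freedom alone.

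**6. Which unit is the cluster (clarification only).** C1 places the sessions directly after baseline: "GMI or CT (4 sessions back-to-back; Week 2". C3 recruits "within 30 months between Year 1, Month 7 and Year 3, Month 12". 186 participants over about 130 weeks is 1.43 per week, against at least 6 per workshop. The documents do not say how weeks map to workshops. Each workshop lies in one arm under any mapping, so clustering remains.

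**The case against.** The strongest objection is that harm is not shown, because no ICC is documented. With groups of 3 and an ICC of 0.02 to 0.05, month-1 type I error at 30% loss is only 5.3–5.8%. C3 also says of the 30% figure: "This conservative attrition estimate is well above the 13% study drop-out rate in" the earlier study. At 13% loss, groups of 3 at those ICCs keep 85–88% power, above the stated 83%. This stands as a limit on the size. It does not rescue the rule: better retention restores power but leaves the standard errors uncorrected, and it slightly enlarges the clusters.

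C5 also does not say in terms that cluster effects are excluded when attendance is similar, the general notation in C12c could hold them, and the team has modelled nesting before. That is fair, and it means the right remedy is already named. But nothing in C12c or C12d applies it unconditionally.

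Three cautions about the numbers also stand. Type I error is given for the month-1 contrast and power for the three-visit mean. The latter is the kind of longitudinal comparison C11 powers; under the same assumptions, month-1 power with 65 per arm is only about 63% before any clustering. The AR(1) structure is inferred and is not the only one that fits. The calculations are Gaussian, whereas many primary outcomes are counts.

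Finally, recruitment also covers Myrtle Beach and Savannah, so weeks and workshops could be crossed. The model would then need a term for each.

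**Conclusion.** The concern holds and should be fixed before analysis. The plan ties the cluster term to an attendance difference, which does not track outcome correlation, and C11 makes no allowance for clustering. That much follows from the text and needs no assumption.

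The size is uncertain. Over assumed ICCs of 0.02 to 0.10, the type I error of an unclustered month-1 test runs from about 5.3% (groups of 3, 30% loss) to 10.2% (groups of 6, 13% loss). At the plan's own 30% loss, power for the longitudinal comparison runs from about 81% down to 61%, depending on ICC, group size and whether the group effect persists. These figures rest on SD = 1, AR(1) correlation 0.5, a Gaussian outcome and loss at random. They are illustrations, not predictions for the count models.

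**What to change.** 1. In C5, delete the attendance trigger and state how recruitment weeks map to workshops. In C12c and C12d, include a random effect for the randomised unit in every Aim I between-arm model: the recruitment week, or the workshop if the two coincide. If a workshop spans several weeks, or a week feeds several workshops, cluster at the higher level or include both; if they are crossed, include both.
2. Base degrees of freedom on the number of clusters. Pre-specify cluster-robust standard errors with a small-sample correction as the fallback if a joint or zero-inflated model does not converge.
3. Restate C11 power over a stated ICC range and cluster size. Include an ICC = 0 row under whichever correlation structure the team used to obtain 83%, and name that structure.
4. As a clarification, give the expected group size. The ceiling of 62 workshops corresponds to 3 per workshop and 6 recruits each to 31 workshops; a ceiling is compatible with fewer, larger groups.

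The cost is SAP wording and one more level in models that are already complex, so the fallback may be needed. The stated power falls and that is accepted. No patients are added.
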